5.4 Case withdrawal and abscission

All enrolled subjects have the right to withdraw from the study at any time. Case withdrawal reasons:

–The subject requested to withdraw and did not want to continue in this study;
–For other reasons, the investigator determined that subjects were not appropriate to continue in the study;

Subjects who dropped out of the study were considered to have fallen out. When the patient falls off, try to contact the patient, complete the evaluation project, and fill in the study summary page.

6. Research methods and procedures

Because this is an observational study, no additional visits or laboratory analysis or evaluation beyond what is required by routine clinical practice are required. The doctor will decide the treatment plan according to the instructions and local regulations. The investigator will review the patient's medical history and laboratory reports to determine eligibility based on inclusion and exclusion criteria. Patients must sign the latest IRB/ IEC-approved informed consent form (ICF) prior to performing data collection. The number and duration of visits are at the discretion of the physician in accordance with local practice.

6.1 Informed consent and inclusion

Subjects who provide informed consent and meet all other inclusion/exclusion

criteria are considered to be enrolled in the study.

6.2 Subject identification number

Each subject was given a unique identification number, namely the initials of the patient and the serial number. The identification numbers of the diabetic group without PAD were: DM001, DM002.....And so on;The identification numbers of PAD groups are DMP001 and DMP002..... And so on;The identification numbers of diabetic foot disease group were: DF001, DF002..... All study documents (such as case report forms, clinical records, etc.) will use this identification number.In addition, under data privacy regulations, a unique identification number is allowed, as long as it does not contain combined information that identifies the subject.

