The inclusion criteria	
 Diagnostic criteria for diabetes: using WHO1999 diabetes diagnostic criteria, that is, (1) having diabetes symptoms (polyuria, polydipsia, and unexplained weight loss), and random (any time after meal) plasma glucose $\geq 11.1 \text{ mmol/L}$ (200 mg/dL); (2), or fasting (fasting for at least 8 hours) plasma glucose $\geq 7.0 \text{ mmol/L}$ (126 mg/dL); (3), or OGTT 2 hours plasma glucose $\geq 11.1 \text{ mmol/L}$ (200 mg/dL) Inclusion criteria of the diabetes PAD group: patients diagnosed as T2DM according to the above-mentioned diagnostic criteria for diabetes, and with (1) symptoms and signs of atherosclerotic occlusion (intermittent claudication, resting pain, reduced or absent pulsation

	
of dorsal foot artery, etc.); (2) Ankle-brachial arterial pressure index (ABI) ≤ 0.9; Toe brachial artery pressure index (TBI) ≤ 0.70; There was no three-phase pulse pattern of foot artery. Transcutaneous partial oxygen pressure (TcPO₂) $< 30 \text{ mmHg}$; (3) Evidence of atherosclerosis, atherosclerotic plaques, arterial stenosis or obstruction in carotid and/or lower extremity major arteries found by vascular color Doppler ultrasound.
 
3. Inclusion criteria for the diabetic foot group caused by PAD: the presence of infection, ulcer and/or deep tissue destruction of the foot was confirmed according to the above diagnostic criteria of diabetic PAD.
 
4. Agree to participate in the study and data collection, and sign the informed consent.

Exclusion criteria	
1. Diabetic ketoacidosis or hyperosmolar state occurs within 30 days;
 
Diabetic coma in 2 or 3 months, or severe hypoglycemia in nearly 1 month;
 
3. Diseases of tumor, immune system and hematopoietic system;
 
4. Other types of diabetes
 
5. Less than 40 years old

Validity analysis	The main observation indexes: II with type 1 diabetes, serum content of heat shock protein 90.
Statistical analysis	
Sample size determination:
 $n = \varphi^2 \left(\sum s_i^2 / g \right) / \left[\sum (\bar{X}_i - \bar{X})^2 / (g - 1) \right]$ 
Statistical analysis: SAS 9.2 statistical analysis software will be used for statistical analysis.

follow-up	No follow-up
Statistical method	Analysis of variance
schedule	
2020-9-1 -- 2020-10-10 Collect all samples
 
2020-10-10 -- 2020-10-15 Complete all sample tests
 
2020-10-15 -- 2020-10-20 Statistical analysis was completed

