6.3 Data source/data collection process

Data from this study were obtained by extracting routine clinical records of enrolled subjects. The investigator was required to complete the study's electronic case report form (eCRF) and/or record form based on the information entered in the patient's medical record throughout the monitoring period.

6.4 Data collection steps:

6.4.1 screening period

- (1) Signed Informed Consent
- (2) Complete inclusion and exclusion criteria verification
- (3) Medical history and demographic data were obtained
- (4) Laboratory tests: screening for diabetes-related complications, blood routine, CRP, coagulation function, renal function, etc

6.4.2 trial

- (1) Serum collection: the nurses collected the patients' fasting blood at 6:00 am in accordance with the routine blood collection procedures: 1 tube of procoagulant blood and 1 tube of anticoagulant blood were collected, each tube was no less than 3ml of blood;Store in a 4-degree

refrigerator for disposal.

(2) Collection of serum and plasma: the blood samples collected by the nurse were placed in a centrifuge, centrifuged at 3000 RPM for 15 minutes, and then the supernatant was collected.

(3) Laboratory test: the collected serum or plasma were quantitatively tested by HSP90 ELISA, and the results were analyzed. The remaining serum or plasma was stored in a negative 80 refrigerator.

6.4.3 follow-up

A telephone interview will be conducted every 3 months to assess the patient's prognosis (blood glucose and medication status, complication progression, PAD or diabetic foot disease).

7. Safety monitoring, reporting and medical treatment

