12.4 Anticipated progress and completion date of the clinical study

2020-9-1 -- 2020-10-10 Collect all samples

2020-10-10 -- 2020-10-15 Complete all sample tests

2020-10-15 -- 2020-10-20 Statistical analysis was completed

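### Subject numbers reveal the severity group, and no group-neutral laboratory code or spread of groups over plates is described for the HSP90 ELISA

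*Protocol*

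**What the plan says.** Protocol section 6.2 assigns subject numbers by severity group:

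- no PAD: "The identification numbers of the diabetic group without PAD were: DM001, DM002"
- PAD: "The identification numbers of PAD groups are DMP001 and DMP002"
- diabetic foot: "The identification numbers of diabetic foot disease group were: DF001, DF002"

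It then rules: "All study documents (such as case report forms, clinical records, etc.) will use this identification number". The same section first defines the number differently, "namely the initials of the patient and the serial number", which does not fit the group prefixes that follow. Section 10.2 allows subjects to be identified by number or initials.

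Section 6.4.2, step (3), covers the assay in one line: "the collected serum or plasma were quantitatively tested by HSP90 ELISA, and the results were analyzed". It gives no label, run order, plate layout or masking. The synopsis names "serum content of heat shock protein 90" as the main observation index and analysis of variance as the method, with 50 subjects in each of three groups. The schedule puts all assays in one window once collection has ended: "2020-10-10 -- 2020-10-15 Complete all sample tests".

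**The concern.** Each group has its own serial sequence, so sorting by subject number sorts by severity group. All 150 samples should be on hand when testing starts, so a sorted run would be easy, and 150 samples are likely to need more than one plate. ELISA readings can shift from plate to plate. If groups sit largely on different plates, that shift enters the group means, and a one-way ANOVA counts it as a group difference.

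A second, smaller risk is that staff who can read the group from the label might handle doubtful readings differently by group. The plate effect needs no intent at all.

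**Working it through.** **Inputs.** From the protocol: three groups of 50, so 3 × 50 = 150 samples; one-way ANOVA; prefixes DM, DMP and DF. Assumed, because the protocol gives no figure: 40 samples per plate (duplicate wells) or 80 (single wells); between-plate SD τ of 0.1 to 0.5 in units of the within-group SD; samples run in the order in which 6.2 lists the groups; nominal level 0.05. The protocol has no figure of its own on assay layout to reproduce.

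**Step 1: layout in that order.**

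- 80 per plate: 50 DM + 30 DMP; 20 DMP + 50 DF.
- 40 per plate: 40 DM; 10 DM + 30 DMP; 20 DMP + 20 DF; 30 DF.

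DM and DF never share a plate. DMP shares a plate with each of them. A strict alphabetical sort would instead run DF, DM, DMP; then DF and DMP never meet and DM is the bridge. The false-positive rates below are unchanged by this, since the groups are exchangeable under no true difference.

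**Step 2: expected between-group mean square with no true difference.** Each group mean carries its plates' effects, weighted by the share of the group on each plate. With within-group variance 1, the expected mean square is 1 + (50/2) × S × τ². S is the sum over plates of (sum of squared weights − squared sum of weights / 3).

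- 80 per plate: weights (1, 0.6, 0) and (0, 0.4, 1). S = (1.36 − 2.56/3) + (1.16 − 1.96/3) = 0.507 + 0.507 = 1.013, giving 1 + 25.3τ².
- 40 per plate: weights (0.8, 0, 0), (0.2, 0.6, 0), (0, 0.4, 0.4), (0, 0, 0.6). S = 0.427 + 0.187 + 0.107 + 0.240 = 0.960, giving 1 + 24τ².

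At τ = 0.2 the between-group mean square is about doubled (2.01 and 1.96).

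**Step 3: simulated false-positive rate.** Two separate simulations, 20,000 runs per scenario; the range is across the two.

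| τ | group order, 40 per plate | group order, 80 per plate | interleaved, 40 / 80 per plate (one simulation) |
|---|---|---|---|
| 0.1 | 0.088–0.090 | 0.089–0.090 | 0.050 / 0.048 |
| 0.2 | 0.205–0.208 | 0.210–0.213 | 0.049 / 0.049 |
| 0.3 | 0.360–0.364 | 0.342–0.347 | 0.040 / 0.043 |
| 0.5 | 0.614–0.620 | 0.547–0.548 | 0.031 / 0.036 |

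With plate positions fully randomised, the second simulation gave 0.048 to 0.052 throughout. Strict interleaving falls below 0.05 at larger τ because plate variation then inflates only the error term; this is a reason to fit plate as well as balance it.

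**Step 4: cost of adjusting after a group-order run.** With plate as a fixed factor, DM versus DF is estimated through DMP. Unadjusted variance: 1/50 + 1/50 = 0.040.

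- 80 per plate: (1/50 + 1/30) + (1/20 + 1/50) = 0.1233; ratio 3.08.
- 40 per plate: (1/10 + 1/30) + (1/20 + 1/20) = 0.2333; ratio 5.83. The plates holding only DM or only DF contribute nothing.

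With groups balanced over plates the ratio is 1.00.

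**The case against.** Section 6.2 speaks of study documents and gives case report forms and clinical records as examples. It does not mention tubes, aliquots or plate maps, and nothing says that samples run in number order. Section 12.1 (item 8) has a designated researcher write implementation rules and SOPs, and section 12.4.2 requires work to institutional SOPs, so coding and layout may be settled there. A plate term is detail that an analysis plan could hold. ELISA is an instrument readout, and the protocol describes no discretionary handling of results. All of this stands, and it makes the plate-confounding part conditional. It does not remove the point, because 6.2 itself fixes a group-revealing number and describes no neutral one, and an analysis plan cannot restore balance once the plates have been run.

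A reader might infer three stronger things that the documents do not support:

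- That no other sample code exists. The text shows only that none is described.
- That plate and group coincide, so the ANOVA cannot separate them. One group always bridges the plates, so every contrast stays estimable with a plate term, at a loss of precision.
- That HSP90 is the sole primary measurement. It is the main observation index in the synopsis, but section 3.1 words the primary endpoint as screening for angiopathy.

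**Conclusion.** The point holds as a cheap safeguard that is missing, not as a demonstrated bias. What the text establishes is a subject number that shows the severity group, required on all study documents, with no neutral laboratory code, masking or plate balancing described ahead of the main measurement. The error rates in the working show what could follow, not what will: they rest on the number being used in the laboratory, a run sorted by it, 40 or 80 samples per plate, and an assumed plate SD. Confidence is medium: high for the numbering scheme, lower for its laboratory consequences.

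**What to change.** In section 6.2, add a group-neutral serial number, one sequence for all subjects, for tubes and laboratory records, with the key held outside the laboratory. Reconcile there the definition by patient initials with the DM/DMP/DF prefixes. In section 6.4.2, step (3), randomise samples to plates so that each plate carries the three groups in near-equal proportion, and include plate as a factor in the ANOVA.

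The cost is a coded label list, a plate map and one model term. No further patients are needed, and there is no delay, because all assays are already scheduled after collection ends. With balanced plates the extra term costs essentially no precision.

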6.3 Data source/data collection process

Data from this study were obtained by extracting routine clinical records of enrolled subjects. The investigator was required to complete the study's electronic case report form (eCRF) and/or record form based on the information entered in the patient's medical record throughout the monitoring period.

6.4 Data collection steps:

6.4.1 screening period

- (1) Signed Informed Consent
- (2) Complete inclusion and exclusion criteria verification
- (3) Medical history and demographic data were obtained
- (4) Laboratory tests: screening for diabetes-related complications, blood routine, CRP, coagulation function, renal function, etc

6.4.2 trial

- (1) Serum collection: the nurses collected the patients' fasting blood at 6:00 am in accordance with the routine blood collection procedures: 1 tube of procoagulant blood and 1 tube of anticoagulant blood were collected, each tube was no less than 3ml of blood;Store in a 4-degree

refrigerator for disposal.

(2) Collection of serum and plasma: the blood samples collected by the nurse were placed in a centrifuge, centrifuged at 3000 RPM for 15 minutes, and then the supernatant was collected.

(3) Laboratory test: the collected serum or plasma were quantitatively tested by HSP90 ELISA, and the results were analyzed. The remaining serum or plasma was stored in a negative 80 refrigerator.

6.4.3 follow-up

A telephone interview will be conducted every 3 months to assess the patient's prognosis (blood glucose and medication status, complication progression, PAD or diabetic foot disease).

7. Safety monitoring, reporting and medical treatment

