List of abbreviations and definitions of terms

Arterial lesions around PAD

OGTT oral glucose tolerance test

1. Research background

Diabetic foot disease is one of the most serious complications of diabetes, which brings great pain and economic burden to patients, with a global incidence of about 6%. In China, the incidence rate is 8.1%, and the amputation rate is 7.3%. Every year, more than 1 million diabetic patients have amputations, ranking first among non-traumatic amputations. According to the American Diabetes Association (ADA), the incidence of Peripheral Arterial Disease (PAD) in diabetic patients is twice that of non-diabetic patients, and the resulting lower limb ischemia is the main cause of the high mortality and disability rate of diabetic foot. According to the International Working Group on Diabetic Foot (IWGDF), about 50% patients with diabetic foot disease are complicated with PAD, and the degree of vascular stenosis is closely related to the prognosis. Severe limb ischemia is a higher cause of diabetic foot ulcer in China than in western countries. The main pathological change of diabetic PAD is atherosclerosis, and endothelial injury is the initial link of atherosclerosis. Oxidative stress is the central link in the mechanism of endothelial injury in diabetic vascular disease, and it is also the basis for us to model endothelial cells with high glucose and hydrogen peroxide.

Heat Shock Protein 90 (Hsp90) is an important type of Heat stress Protein. The molecular size of Hsp90 is 90-kDa. In eukaryotic cells, there are mainly two subtypes, α and β , and the content of Hsp90 accounts for 2–3% of the total Protein in cells. Involves in the correct folding and activation of intracellular proteins. Although Hsp90 is primarily involved in intracellular protective mechanisms, they can also be exposed to the plasma membrane and released in the extracellular space, resulting in detectable levels of Hsp90 in the blood. Extracellular heat shock proteins are involved in cell-cell

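### Section 6.4.2 puts freezing after the ELISA while the schedule tests after collection, so as written samples stay unfrozen for 0 to 44 days depending on enrolment date

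*Protocol*

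**What the plan says.** Protocol section 6.4.2 sets out specimen handling in three numbered steps.

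- **Step (1), blood draw.** Two tubes are taken fasting at 6:00 am. The storage instruction is attached to these tubes: "each tube was no less than 3ml of blood;Store in a 4-degree" (the sentence goes on to name a refrigerator).
- **Step (2), separation.** The samples are "centrifuged at 3000 RPM for 15 minutes, and then the supernatant was collected". No time from draw to spin is set, and no storage condition is given for the supernatant.
- **Step (3), assay, then freezing.** First, "the collected serum or plasma were quantitatively tested by HSP90 ELISA, and the results were analyzed". Then, "The remaining serum or plasma was stored in a negative 80 refrigerator". This is the only mention of minus 80.

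Section 12.4 (anticipated progress and completion date) gives the timetable: "2020-9-1 -- 2020-10-10 Collect all samples", followed by "2020-10-10 -- 2020-10-15 Complete all sample tests". The schedule row of the summary table repeats the same dates. The summary table also names serum HSP90 as the main observation index and plans 50 patients in each of three groups (no PAD, PAD, diabetic foot disease).

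**The concern.** Taken alone, each part is unremarkable. An ELISA run soon after the spin, with the leftover frozen, is a workable sequence. A single batch assay at the end of collection is also workable, if samples are frozen while they wait. The plan combines the first sequence with the second timetable. Staff who follow the steps and dates as written have no instruction to freeze anything before the assay, although the first samples are drawn more than five weeks before the testing window opens.

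Time to assay then depends on when a patient was enrolled. If measured HSP90 changes during unfrozen storage, that time becomes a source of variation in the one variable the study compares. If enrolment timing is similar in the three groups, the result is extra noise and lost precision. If one group is enrolled earlier than another, part of any difference between groups could be a difference in storage. Handling cannot be repaired once the samples have been collected.

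**Working it through.** **1. Time from draw to assay.** The inputs are the dates in section 12.4; it is assumed that no assay is run before 10 October. The protocol states no storage duration, so there is no planned figure to reproduce.

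| Draw date | Assay on 10 October | Assay on 15 October |
|---|---|---|
| 1 September | 39 days | 44 days |
| 10 October | 0 days | 5 days |

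For a common assay day the wait differs by up to 39 days between patients. With even enrolment (an assumption) the mean wait is 39/2 = 19.5 days if all are assayed on 10 October, and 19.5 + 5 = 24.5 days if all are assayed on 15 October.

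**2. Noise, if the groups enrol alike.** The drift rate r is not in the documents; take 0.01, 0.02 and 0.03 SD of HSP90 per day. With even enrolment over 39 days, storage time has variance 39²/12 = 126.75 days². The added within-group variance, as a share of SD², is 126.75 × r²:

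- r = 0.01: 0.0127, about 1%
- r = 0.02: 0.0507, about 5%
- r = 0.03: 0.1141, about 11%

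**3. Bias, if the groups enrol at different times.** Let g be the gap in mean storage, in days, between the two extreme groups, with the third group midway. The spurious difference between the extremes is d = g × r in SD units. With n = 50 per group the noncentrality of the one-way analysis of variance is

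λ = 50 × [(d/2)² + 0 + (d/2)²] = 25d².

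The test has 2 and 147 degrees of freedom; the critical F at the 5% level is 3.058. The 5% level is also an assumption, because the protocol states none. The false-positive rate is the chance that a noncentral F exceeds 3.058.

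| Gap g | Drift r | d | λ | False-positive rate |
|---|---|---|---|---|
| 5 days | 0.01 | 0.05 | 0.0625 | 5.5% |
| 5 days | 0.02 | 0.10 | 0.25 | 6.9% |
| 5 days | 0.03 | 0.15 | 0.5625 | 9.4% |
| 10 days | 0.01 | 0.10 | 0.25 | 6.9% |
| 10 days | 0.02 | 0.20 | 1.00 | 13.1% |
| 10 days | 0.03 | 0.30 | 2.25 | 24.5% |

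**4. What gaps are attainable.** Suppose all groups open on 1 September and accrue evenly, the slowest takes the full 39 days and the fastest fills its 50 places in x days. The mean enrolment days are 39/2 and x/2, so g = 19.5 − x/2. A 5-day gap needs x = 29 and a 10-day gap needs x = 19. The ceiling is 19.5 days, reached only if one group fills at once.

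**The case against.** The strongest objection is that the protocol does not say samples sit at 4 degrees for weeks. A reader might infer that from 4 degrees being the only temperature named before the assay. However, the instruction in step (1) covers the drawn tubes before centrifugation, and the temperature of the separated serum or plasma is not stated. This stands: the text supports samples being unfrozen as sequenced, not six weeks at a known temperature.

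The text is also a translation, and too much can be read into the order of its sentences. The wording on the remainder does not strictly forbid freezing beforehand, and a window for completing the tests does not strictly exclude earlier runs. This stands as a limit on certainty. Still, a separate testing window that opens when collection closes reads most naturally as batch testing, and nothing in the three steps tells staff to freeze first.

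Section 12.1 has a designated researcher write the implementation rules and SOPs and requires reliable laboratory results, and section 12.4.2 requires work to follow the institution's SOP. Holding times often sit in such documents. This stands only in part. The protocol itself fixes draw time, volume, spin and the order of assay and freezing, and an SOP that froze before assay would depart from that written order.

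A reader might also point to section 1, where "the content of Hsp90 accounts for 2–3% of the total Protein in cells", and argue that blood cells leak HSP90 into the sample during the wait. Leakage from cells depends on time from draw to spin and ends at separation, whereas the 39 to 44 days run from draw to assay. The protocol does not say that unspun blood is kept for weeks. Leakage would raise the reading and degradation would lower it, so no direction of error is established.

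Finally, the drift rates and group gaps are assumed. The protocol contains no accrual forecast by group and no stability data. This stands, and the error rates above are illustrations only.

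**Conclusion.** The concern holds in a limited form. The stated handling sequence and the stated schedule do not fit together: freezing is assigned only to what remains after the assay, while the assay is placed after collection ends. Assuming no testing before 10 October, the unfrozen wait runs from 0 to 44 days and is set by enrolment date.

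The certain consequence is an uncontrolled handling time in the measurement of the main index. How much that matters depends on a drift rate that the documents do not give. Over the assumed range, the cost with similar enrolment across groups is about 1% to 11% extra within-group variance. A reader might infer that the group comparison is biased. The documents do not support that, because nothing in them says that the groups enrol at different times. If they did, the false-positive rate would be 5.5% to 9.4% for a 5-day gap and 6.9% to 24.5% for a 10-day gap. A gap of 20 days would exceed the 19.5-day ceiling under common opening and even accrual, so no figure is claimed for it.

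The point is worth correcting before the first sample is drawn. If the laboratory already intends to freeze before the assay, the written sequence is wrong and needs correcting all the same.

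**What to change.** Amend section 6.4.2 so that:

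- every tube is centrifuged within one fixed interval on the day of draw;
- the serum or plasma is aliquoted and frozen at minus 80 before the assay;
- all aliquots are assayed together in the 10 to 15 October window;
- draw, spin and freeze times are recorded for each sample, so that handling can be compared between groups.

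The cost is same-day aliquoting by the laboratory and one freeze-thaw cycle for every sample, which at least is the same for all three groups. The schedule need not change, and minus 80 storage is already in the plan.
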